6.7. Dose Modification

Dose modifications are not planned in this study.

6.8. Treatment of Overdose

For this study, any dose of study drug greater than the prescribed daily dose will be considered an overdose. There is no specific treatment recommended to treat an overdose of study drug and the subject should receive treatment directed towards any symptoms manifested.

In the event of an overdose, the Investigator should:

1. Contact the Medical Monitor as soon as possible.
2. Closely monitor the subject for any AE/SAE and laboratory abnormalities.
3. Document the quantity of the excess dose as well as the duration of the overdose.

Decisions regarding dose interruptions or modifications will be made by the Investigator in consultation with the Medical Monitor based on the clinical evaluation of the subject

6.9. Intervention after the End of the Study

No additional intervention is planned beyond the end of the study.

7. DISCONTINUATION OF STUDY DRUG AND SUBJECT DISCONTINUATION/WITHDRAWAL

7.1. Stopping Rules

Given severity of illness in COVID-19, there are no pre-specified stopping rules for this study as a whole. Instead there will be close oversight by the Sponsor and DMC reviews for safety as specified in [Section 9.5.1](#).

7.1.1. Pregnancy

A subject must permanently discontinue study drug if she becomes pregnant. See Appendix 4 ([Section 10.4](#)) and [Section 8.3.5](#) for additional details.

See the SoA ([Section 1.2](#)) for data to be collected at the time of study drug discontinuation and follow-up, and for any further evaluations that need to be completed.

7.2. Discontinuation of Study Drug

In some instances, it may be necessary for a subject to permanently discontinue study drug. Please also refer to stopping rules described in [Section 7.1](#).

Permanent discontinuation of study drug does not mean withdrawal from the study, and the subject will be encouraged to remain in the study and continue to complete all study visits. See the SoA ([Section 1.2](#)) for data to be collected at the time of drug discontinuation and follow-up and for any further evaluations that need to be completed.

Subjects may discontinue or be discontinued from study drug at any time. A subject may discontinue study drug for reasons including but not limited to:

- Adverse event
- Death
- Lost to follow-up
- Non-compliance with study drug
- Physician decision
- Pregnancy
- Lack of efficacy
- Protocol deviation
- Study terminated by Sponsor
- Withdrawal by subject* (*only for discontinuing study drug, but will remain in study)

The reason for subject discontinuation from study drug will be recorded in the eCRF. At the time of treatment completion or study drug discontinuation, the EOT/ET visit should be completed as shown in the SoA ([Section 1.2](#)). Subjects should continue to be followed for safety even if they discontinue study drug prematurely unless they withdraw consent.

Pregnancy is a mandatory criterion for permanent discontinuation of study drug (see [Section 7.1.1](#)).

7.3. Withdrawal from the Study

Subjects have the right to withdraw from the study at any time and for any reason without prejudice to their future medical care by the Investigator or at the institution. A subject may withdraw from the study for reasons including but not limited to:

- Death
- Withdrawal by subject
- Lost to follow-up
- Study terminated by Sponsor

The reason for subject withdrawal from the study will be recorded in the eCRF.

At the time of withdrawal from the study, the end of study visit should be completed, as shown in the SoA ([Section 1.2](#)).

If the subject withdraws consent for disclosure of future information, the Sponsor may retain and continue to use any data collected before such a withdrawal of consent.

If a subject withdraws from the study, he/she may request destruction of any samples taken and not tested, and the Investigator must document this in the site study records.

7.4. Lost to Follow up

A subject will be considered lost to follow-up if he or she repeatedly fails to return to the study site or be contacted remotely for scheduled outpatient visits post hospital discharge.

The following actions must be taken if a subject fails to return to the clinic and/or be available for remote contact for a required study visit:

- The site must attempt to contact the subject and reschedule the missed visit as soon as possible and counsel the subject on the importance of maintaining the assigned visit schedule and ascertain whether or not the subject wishes to and/or should continue in the study.
- Before a subject is deemed lost to follow up, the Investigator or designee must make every effort to regain contact with the subject (where possible, 3 telephone calls and, if necessary, a certified letter to the subject's last known mailing address or local equivalent methods). These contact attempts should be documented in the subject's medical record.
- Should the subject continue to be unreachable, he/she will be considered to have withdrawn from the study.

Discontinuation of specific sites or of the study as a whole are handled as part of Appendix 1 ([Section 10.1.8](#)).

8. STUDY ASSESSMENTS AND PROCEDURES

- Study procedures and their timing are summarized in the SoA ([Section 1.2](#)). Protocol waivers or exemptions are not allowed.
- Immediate safety concerns should be discussed with the Sponsor immediately upon occurrence or awareness to determine if the subject should continue or discontinue study drug.
- Adherence to the study design requirements, including those specified in the SoA, is essential and required for study conduct.
- All screening evaluations must be completed and reviewed to confirm that potential subjects meet all eligibility criteria. The Investigator will maintain screening information including details of all subjects screened and to confirm eligibility or record reasons for screening failure, as applicable.
- Missed visits should be avoided if at all possible; if a visit is missed and cannot be rescheduled, the subject should resume their original visit schedule at the next scheduled visit. In case of natural disasters or pandemics, some visits/study procedures can be done via virtual visits or at home visits when discharged. Refer to study reference manual for more details.

8.1. Efficacy Assessments

8.1.1. Oxygenation Measures

Peripheral capillary oxygen saturation (SpO₂) with pulse oximeter will be used as surrogate for arterial blood oxygen saturation. While hospitalized, the SpO₂ will be measured twice a day (morning and night). Measurement is to be done with the subject laying supine or with the head of the bed inclined, unless indicated otherwise; the same position should be used throughout the study and the subject's position will be captured in the eCRF. The FiO₂ at the time of each SpO₂ measurement (morning and night while hospitalized) must also be recorded in the eCRF.

Peripheral hemoglobin oxygen saturation to inspired oxygen fraction (SpO₂/FiO₂) will also be measured. Oxygenation will be assessed using the categories in [Table 4](#).

Table 4: A 4-Point Oxygen Ordinal Scale for Severity Categories by SpO₂/FiO₂ Ratio

Score	Severity	SpO ₂ /FiO ₂ (mmHg)
0	None	> 315
1	Mild	> 235 to 315
2	Moderate	> 150 to 235
3	Severe	≤ 150

8.1.2. Measure of Clinical Support

At each study day while hospitalized, the following measure of clinical support should be assessed:

- Oxygen requirement
- Non-invasive mechanical ventilation (via mask)
- Mechanical ventilator requirement (via endotracheal tube or tracheostomy tube) or Extracorporeal membrane oxygenation (ECMO) requirement
- Level of consciousness: alert vs. (arousable only to voice or pain or unresponsive)

In addition, date of hospital discharge readiness or date of hospital discharge (if different) will be collected.

8.1.3. Clinical Status Ordinal Score

Clinical status will be assessed using the 6-point ordinal score (Table 5). The ordinal scale is an assessment of the clinical status at the first assessment of a given study day. Each day, the worse score for the previous day will be recorded. i.e. on day 3, day 2 score is obtained and recorded as day 2. This scale has been used successfully as an endpoint for evaluation of treatments for severe influenza requiring hospitalization (Peterson, 2017).

Table 5: A 6-Point Ordinal Score for Assessing Clinical Status

Score	Description
1	Not hospitalized
2	Hospitalized, not requiring supplemental oxygen
3	Hospitalized, requiring supplemental oxygen
4	Hospitalized, on non-invasive ventilation or high flow oxygen devices
5	Hospitalized, on invasive mechanical ventilation or ECMO
6	Death

8.1.4. National Early Warning Score (NEWS)

The NEWS has demonstrated an ability to discriminate subjects at risk of poor outcomes. (Smith, 2016; Williams, 2019). This score is based on 7 clinical parameters, vital signs (respiratory rate, temperature, blood pressure, and heart rate), SpO₂, breathing room air or supplemental oxygen, and consciousness (Table 6). The NEWS is being used as an efficacy measure.

NEWS will be derived from other parameters to be collected during the study as specified in SoA (Section 1.2).

Table 6: NEW Score

PHYSIOLOGICAL PARAMETERS	3	2	1	0	1	2	3
Respiration Rate	≤8		9 - 11	12 - 20		21 - 24	≥25
Oxygen Saturations	≤91	92 - 93	94 - 95	≥96			
Any Supplemental Oxygen		Yes		No			
Temperature	≤35.0		35.1 - 36.0	36.1 - 38.0	38.1 - 39.0	≥39.1	
Systolic BP	≤90	91 - 100	101 - 110	111 - 219			≥220
Heart Rate	≤40		41 - 50	51 - 90	91 - 110	111 - 130	≥131
Level of Consciousness				A			V, P, or U

Level of consciousness: alert (A), arousable only to voice (V), or pain (P) and unresponsive (U)

8.1.5. Hospital Discharge Readiness Criteria

The subject’s readiness for hospital discharge will be evaluated based on the following criteria (must meet all):

- Normal O₂ saturation on room air or a return to pre-morbid status
- Afebrile
- Able to ambulate (or use commode) without assistance or a return to pre-morbid mobility (for non-ambulatory subjects)
- Able to dress self or a return to pre-morbid status
- Eating pre-morbid full diet or a return to pre-morbid status

Date of actual hospital discharge and date of any readmission during the study period should be captured. Subjects’ oxygen supplementation status at hospital discharge will also be captured (with vs. without oxygen supplementation).

8.1.6. Antiviral Activity

Quantitative viral load using nasopharyngeal swab/sputum SARS-CoV-2 PCR will be used to monitor disease status during the study. For more details refer to the laboratory manual.

8.2. Safety Assessments

Planned time points for all safety assessments are provided in the SoA ([Section 1.2](#)).

8.2.1. Physical Examinations

- Physical examinations will be performed by the principal investigator, a designated sub-investigator or a qualified hospital care staff member.
- A complete physical examination will include, at a minimum, assessments of the skin, cardiovascular system, respiratory system, abdomen (gastrointestinal, liver and spleen) and neurological system. Height and weight will also be measured and recorded.
- A symptom-directed physical examination will include, at a minimum, assessments of the skin, respiratory system, cardiovascular system, and abdomen (liver and spleen).

8.2.2. Vital Signs

- Blood pressure, heart rate, and respiratory rate will be measured after the subject has been resting for 5 minutes.
- Temperature will be recorded twice daily while hospitalized (morning and evening)
- Vital signs will be measured prior to any blood draw that occurs at the same timepoint

8.2.3. Electrocardiograms

12-lead ECG will be obtained while subject is in supine position using an ECG machine that automatically calculates the heart rate and measures PR, QRS, and QT (QTcF), intervals. Subject to be resting for at least 2 minutes prior to ECG.

8.2.4. Clinical Safety Laboratory Assessments

- See Appendix 2 ([Section 10.2](#)) for the list of clinical laboratory tests to be performed and to the SoA for the timing and frequency.
- The Investigator must review the laboratory report, document this review, and record any clinically significant adverse changes occurring during the study in the AE section of the eCRF. The laboratory reports must be filed with the source documents.
- All laboratory tests with values considered clinically significant during participation in the study or within 11 days after the last dose of study drug should be repeated until the values return to normal or baseline or are no longer considered clinically significant by the Investigator or Sponsor's Medical Monitor/designee.
 - If such clinically significant values do not return to normal/baseline within a period of time judged reasonable by the Investigator, the etiology should be identified, and the Sponsor notified.

- All protocol-required laboratory assessments, as defined in [Appendix 2](#), must be conducted in accordance with the laboratory manual and the SoA.
- If laboratory values from non-protocol specified laboratory assessments performed at the institution’s local laboratory require a change in subject management or are considered clinically significant by the Investigator (e.g., SAE or AE or dose modification), then the results must be recorded in the eCRF.

8.3. Adverse Events and Serious Adverse Events

The definitions of an AE and SAE can be found in Appendix 3 ([Section 10.3](#)).

All AEs will be reported by the subject (or, when appropriate, by a caregiver, surrogate, or the subject's legally authorized representative).

The Investigator and any qualified designees are responsible for detecting, documenting, and recording events that meet the definition of AE, SAE.

All AEs will be classified for severity using the common terminology criteria for AEs (CTCAE) V.5.

8.3.1. Time Period and Frequency for Collecting AE and SAE Information

[Table 7](#) below summarizes the different reporting periods for AEs and SAEs.

Table 7: Adverse Event Reporting Periods

Type of Event	Adverse Event	Serious Adverse Event
Reporting period	From consent until Day 28 visit (at least 18 days after last dose of study drug).	From consent until Day 28 visit (at least 18 days after the last dose of study drug). SAEs will be recorded for study drug and for remdesivir.
Reporting Timelines to the Sponsor	Entered into the clinical database on an ongoing basis	Within 24 hours of site awareness

Medical occurrences that begin before the start of study drug but after obtaining informed consent will be recorded on the Adverse Events section of the case report form (CRF) and will be identified in the analysis as non-treatment-emergent adverse events (non-TEAEs).

All SAEs (for study drug and for remdesivir) will be recorded and reported to the Sponsor or designee immediately and under no circumstance should this exceed 24 hours from site awareness, as indicated in Appendix 3 ([Section 10.3](#)). The Investigator will submit any updated SAE data to the Sponsor or designee within 24 hours of it being available.

Investigators are not obligated to actively seek AEs or SAEs after conclusion of the study participation. However, if the Investigator learns of any SAE, including a death, at any time after a subject has been discharged from the study, and he/she considers the event to be related to the study drug or study participation, the Investigator must promptly notify the Sponsor or designee.

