9.4.3. Safety and Tolerability Analyses

All safety analyses will be performed on the Safety Analysis Set. AEs will be coded using the most current Medical Dictionary for Regulatory Activities (MedDRA[®]). The number of subjects

experiencing TEAEs) and number of individual TEAEs will be summarized by treatment, system organ class and preferred term. TEAEs will also be summarized by severity and by relationship to study drug. Serious TEAEs (SAEs) and TEAEs leading to discontinuation of study drug will be summarized by treatment, system organ class and preferred term.

Laboratory evaluations, vital signs assessments and ECG parameters will be summarized by treatment and protocol specified collection time point.

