- The Investigator is obligated to perform or arrange for the conduct of supplemental measurements and/or evaluations as medically indicated or as requested by the Sponsor or designee to elucidate the nature and/or causality of the AE or SAE as fully as possible. This may include additional laboratory tests or investigations, histopathological examinations, or consultation with other health care professionals.
- If a subject dies during participation in the study or during a recognized follow-up period, the Investigator will provide the Sponsor with a copy of any postmortem findings including histopathology, if available.
- New or updated information will be recorded in the originally completed CRF.
- The Investigator will submit any updated SAE data to the Sponsor or designee within 24 hours of receipt of the information.

10.3.4. Reporting of SAEs**SAE Reporting to Medical Monitor via an Electronic Data Collection Tool**

- The primary mechanism for initial reporting of an SAE to Sponsor or designee will be the electronic case report form (eCRF).
- If the eCRF is unavailable, then the site will use the paper SAE data collection tool (see next section) in order to report the event within 24 hours.
- The site will enter the SAE data into the eCRF as soon as it becomes available.
- After the study is completed at a given site, the eCRF will be taken off-line to prevent the entry of new data or changes to existing data.
- If a site receives a report of a new SAE from a study subject or receives updated data on a previously reported SAE after the electronic data collection tool has been taken off-line, then the site can report this information on a paper SAE form (see next section) or to the Medical Monitor by telephone.
- Contacts for SAE reporting can be found in the relevant site manual.

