1.1. Objectives and Endpoints

Objectives	Endpoints
Primary	

 To evaluate clinical benefit of BLD-2660 in hospitalized adults with recently diagnosed SARS-CoV-2 infection 	
 Time to recovery as defined by no longer requiring oxygen support or hospital discharge, whichever occurs first

 To evaluate improvement in oxygenation in hospitalized adults with COVID-19 treated with BLD-2660 	
 Change from baseline to Day 10 or hospital discharge, if sooner, in the ratio of peripheral hemoglobin oxygen saturation to fraction of inspired oxygen (SpO₂/FiO₂)
Secondary	

 To evaluate the safety and tolerability of BLD-2660 in the same population 	
 Incidence of TEAEs and serious adverse events (SAEs)

 To evaluate improvement in Biomarkers 	
 Change from baseline to Days 10/EOT, 14, 21 and 28 in serum calprotectin

 Additional efficacy outcomes 	
 Time to hospital discharge readiness Proportion of participants reporting each 6-point ordinal scale of the clinical status outcome assessment Change from baseline to Days 10/EOT, 14, 21 and 28 in IL-6 and D-dimer

Objectives	Endpoints
Exploratory	

 Other efficacy outcomes 	
 Proportion of participants who require mechanical ventilation after study entry

 To evaluate antiviral activity of BLD-2660 in the same population 	
 Change from baseline in SARS-CoV-2 viral load at Days 5, 10/EOT, 14, and 28

 Other safety outcomes 	
 Clinically relevant changes from baseline in electrocardiogram (ECG), and clinical laboratory values at each post baseline time point Proportion of participants with clinically significant drug-related troponin elevations that have repeat elevation upon confirmatory testing as adjudicated by the DMC while continuing study drug during the 10-day treatment period

 To assess population pharmacokinetics (PK) characteristics of BLD-2660 	
 BLD-2660 plasma concentrations

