5.8.2. Adverse Events

Adverse events will be coded using the Medical Dictionary for Regulatory Activities (MedDRA). All AEs that occur on or after the date of first dose of study intervention will be considered Treatment Emergent Adverse Events (TEAEs), and will be summarized using frequency counts and percentages, with the number of participants in the safety set used as the denominator.

Summaries of TEAEs will be presented by treatment group, and overall, using the MedDRA level hierarchy (system organ class and preferred term) as follows:

- Overall TEAEs (i.e., regardless of intensity or relationship to treatment)
- TEAEs by NCI CTCAE intensity grade (Grade 1, 2, 3, 4, 5)
- TEAEs by relationship to study medication (related, not related)
- TEAEs leading to permanent discontinuation of study medication (i.e., action taken is drug withdrawn)
- TEAEs leading to permanent discontinuation of study medication (i.e., action taken is drug withdrawn) by relationship to study medication
- Serious TEAEs (SAEs)
- SAEs by relationship to study medication (related, not related)

Unless otherwise specified, at each level of summarization a participant will be counted once if they reported one or more events at that level of summarization. If more than one occurrence of an event is reported, the event of the worst intensity or the worst-case relationship assessment will be summarized.

In the case of an incomplete AE start date, determining if an AE is treatment emergent will be based on the following rules. If the day is missing and the month and year of an onset date are provided and on or after the date of randomization, the following rules will be applied.

- If month/year of the onset date is on or after the month/year of randomization, the AE will be considered treatment emergent.
- If month/year of the onset date is equal to the month/year of randomization, and the end date is present, the end date will be used to determine when the AE started. If the end date is on or after randomization, the AE will be considered treatment emergent; otherwise, if the AE stopped before randomization, then it will not be considered treatment emergent.
- If month/year of the onset date is equal to the month/year of randomization, and the end date is a partial date, the AE will be considered treatment emergent.

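### Treatment emergence is decided by onset alone, so an AE recorded between consent and first dose that worsens or turns serious on study drug can drop out of the by-arm AE and SAE tables

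*Protocol*

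**What the plan says.** **Classification.** Protocol 8.3.1 deals with the gap between consent and dosing: "Medical occurrences that begin before the start of study drug but after obtaining informed consent will be recorded on the Adverse Events section", and these "will be identified in the analysis as non-treatment-emergent adverse events (non-TEAEs". SAP 5.8.2 gives the working definition: "All AEs that occur on or after the date of first dose of study intervention will be considered Treatment Emergent Adverse Events (TEAEs".

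**Tables.** SAP 5.8.2 introduces its list of AE tables with "Summaries of TEAEs will be presented by treatment group, and overall, using the MedDRA level hierarchy". The SAE line in that list reads "Serious TEAEs (SAEs". Protocol 9.4.3 is the same: "Serious TEAEs (SAEs) and TEAEs leading to discontinuation of study drug will be summarized by treatment, system organ class and preferred term".

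**Endpoint and collection.** The secondary safety endpoint in SAP 1.1, also in Protocol section 3, is "Incidence of TEAEs and serious adverse events (SAEs". Table 7 in Protocol 8.3.1 collects both AEs and SAEs from consent to the Day 28 visit.

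**Recording.** On follow-up of AEs and SAEs, Protocol 10.3.3 says: "New or updated information will be recorded in the originally completed CRF".

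**The concern.** By-arm safety tables exist to show what changed once study drug began. An event that starts during screening at a low grade and becomes severe or serious after dosing is such a change. If emergence is read from the onset date alone, and the onset date stays on the pre-dose side, the event is in the database but not in the tables that compare the arms.

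Two things are at stake. One is the count of on-drug AEs and SAEs by arm, which would be too low for these events. The other is agreement between endpoint and analysis: the endpoint names SAEs without qualification, while the only SAE tables described are of treatment-emergent ones.

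**Working it through.** The documents give no figure to reproduce, so the check is a comparison of text, followed by an illustration on assumed rates.

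1. **Is onset really the test?** Protocol 8.3.1 turns on when the occurrence begins. The SAP definition says occur rather than start, but its rules for incomplete dates, also in 5.8.2, work from the AE onset date. Onset is therefore the operative criterion in both.
2. **Is there a worsening clause?** None appears in Protocol 8.3.1, 9.4.3 or 10.3, or in SAP 5.8.2. The incomplete-date rules can bring in an event through its end date or by default, but only when the start date is partial. They cut at randomization rather than first dose.
3. **Does the worst-intensity rule help?** SAP 5.8.2 reports the worst grade when an event is reported more than once. That rule works within the TEAE summaries and cannot bring in an event already classed as non-TEAE.
4. **Does a change create a new onset?** Protocol 10.3.3 directs updates to the existing record. Protocol 10.3.2 treats an event as serious once it meets a serious criterion and asks for no new onset. The pre-dose start date therefore stays, unless the site opens a new record.
5. **Worked case.** A Grade 1 AE is recorded on Day -2 and reaches Grade 4, or becomes serious, on Day 4. Under Protocol 8.3.1 it is a non-TEAE, and under SAP 5.8.2 its onset precedes the first-dose date. Kept on one record, it enters none of the listed by-arm tables (overall, grade, relationship, discontinuation, SAE).
6. **Day 1.** An event on Day 1 before the first capsule is a non-TEAE under the protocol and a TEAE under the SAP, which compares dates only.

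**Illustration of size (both rates assumed).** Subjects affected = P(AE between consent and first dose) × P(that AE worsens on drug). Take 5–20% for the first and 10–50% for the second:

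- Low: 0.05 × 0.10 = 0.5%, which is 0.4 of 80 active and 0.2 of 40 control.
- High: 0.20 × 0.50 = 10%, which is 8 of 80 active and 4 of 40 control.
- Capping the second rate at 30%: 0.20 × 0.30 = 6%, which is 4.8 of 80 and 2.4 of 40.

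The range spans a factor of 20 (10% / 0.5%) on assumptions alone. It also does not subtract cases where the site enters the worsening as a new AE. It shows the arithmetic and is not an estimate.

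**The case against.** The best case against the point is that the protocol already captures most on-drug worsening. Protocol 10.3.1 counts exacerbated disease as an AE. It covers clinically significant laboratory, ECG and vital-sign abnormalities that get worse than baseline, and conditions first detected after dosing. Protocol 8.2.4 sends clinically significant adverse laboratory changes to the AE section. A site following these could enter a worsening as a new AE with a post-dose onset, and it would then be counted.

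The window is also short. Screening is up to 3 days, and the Schedule of Activities shows AE review only from baseline, although Table 7 collects from consent. Expected COVID-19 progression is generally not an AE. Other by-arm outputs remain: laboratory, vital-sign and ECG summaries (SAP 5.8.3 to 5.8.5), discontinuation reasons (5.4), the ordinal scale including death (5.6.2) and mechanical ventilation (5.7). Table and listing specifications are in a separate document, so a listing of non-TEAEs may exist. The rule is the same in both blinded arms.

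Most of this stands, and it rules out some stronger readings that a reader might infer:

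- *Pre-existing abnormalities in hospitalised patients make this a main route of missed toxicity.* Not supported. Worsening of findings present before consent can be a new AE under Protocol 10.3.1.
- *The worsening appears in no by-arm output.* Too broad. The gap is in the AE and SAE tables.
- *The Day 1 mismatch understates safety.* It does not. The SAP introduction says the SAP prevails, and its date rule counts more events.

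The core gap remains. No text requires a new record for an AE already entered after consent, and the recording instruction points the other way, so the count would depend on site habit. The laboratory, vital-sign and ECG sections also leave clinically significant findings to be read from the AE summaries, which are the TEAE tables. A listing is not a comparison by arm.

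**Conclusion.** The point holds in a limited form. Emergence is set by onset, all by-arm AE and SAE tables are restricted to TEAEs, and an AE from the interval between consent and the first-dose date that later rises in grade or becomes serious is left out of them if it stays on its original record. This is a stated rule that gives the wrong count, and it leaves the SAE part of the secondary endpoint without a matching table.

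Confidence is high on the text and low on the size. The number is probably small, and the conclusion depends on sites updating the existing record, which eCRF guidance outside these documents could change. A reader might infer a material loss of precision: with 80 active subjects, going from 0 to 2 events moves the one-sided 95% upper bound from 3.7% to 7.7%. That needs both missed events to be in the active arm and of the same type, which nothing in the documents shows. Bias between the arms is not shown either. The Day 1 difference is a matter of consistency only.

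**What to change.** 1. In SAP 5.8.2, with Protocol 8.3.1 amended to match, define a TEAE as an AE that starts on or after first dose, or that starts earlier and increases in CTCAE grade or becomes serious on or after first dose.
2. Use first dose as the cut throughout, including the incomplete-date rules that now use randomization. Align the Day 1 rule in the two documents at the same time.
3. Add a by-arm summary of all SAEs from consent with the treatment-emergent ones marked. This matches the endpoint, and the marking keeps pre-dose events from being read as drug effects.

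The cost is wording, minor reprogramming and some data queries to date the worsening, since SAP 5.10 reports that enrolment is complete. TEAE counts may rise slightly. SAP 5.10 also plans a Phase 3 part under an amendment of this protocol, so correcting the definition now avoids carrying it forward.
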